1. INTRODUCTION

This statistical analysis plan (SAP) contains definitions of analysis sets, derived variables, and statistical methods for the study CNTO136MDD2001.

1.1. Trial Objectives

Primary Objective

To evaluate the efficacy of sirukumab as adjunctive treatment to antidepressant therapy (monoaminergic antidepressant) where sirukumab (administered as a 50mg subcutaneous (SC) injection at Day 1, Day 28 and Day 56 during the 12-week double-blind treatment period) is compared to adjunctive placebo based on the change from baseline to 12-week endpoint in depressive symptoms as measured by the total score on the Hamilton Depression Rating Scale (HDRS₁₇), in subjects diagnosed with Major Depressive Disorder (MDD) who have had a suboptimal response to the current standard oral antidepressant therapy and have a screening high sensitivity C-Reactive Protein (hsCRP) \geq 0.300 mg/dL (International System of Units (SI) 3.00 mg/L).

Secondary Objectives

The secondary objectives are to include the evaluation of the impact of treatment with adjunctive sirukumab compared to adjunctive placebo, on: (1) overall safety and tolerability (2) anhedonia (as measured by the change in the Snaith Hamilton Pleasure Scale [SHAPS] from baseline to week 12) (3) global severity of symptoms of MDD (as measured by the change in the Clinical Global Impression - Severity [CGI-S] scale from baseline to Week 12) (4) remission (HDRS₁₇ total score \leq 7) and response rates (\geq 50%) improvement in HDRS₁₇ total score from baseline) at 12-week end point (5) subjectreported severity of symptoms of MDD (as measured by the change in the Patient Health Questionnaire [PHQ-9] from baseline to Week 1 and to Week 12) (6) fatigue (as measured by the change in the Functional Assessment of Chronic Illness Therapy-Fatigue [FACIT Fatigue] scale from baseline to Weeks 1, 4, 8 and 12) and (7) to evaluate the efficacy measured by change in the HDRS17 scores following adjunctive sirukumab compared to adjunctive placebo in the Treatment Resistant Depression (TRD) versus non-TRD subjects. (8) Evaluate pharmacokinetics and immunogenicity of sirukumab in subjects with MDD. (9) Evaluate the impact of treatment with adjunctive sirukumab in subjects with screening hsCRP \geq 3.00 mg/L and in those with screening hsCRP<3.00 mg/L based on changes from baseline to Week 12 in HDRS₁₇ total score. (10) Assess the efficacy of sirukumab compared to placebo as adjunctive therapy to an antidepressant in subjects with MDD with screening hsCRP levels <0.300 mg/dL versus those with screening hsCRP levels ≥ 0.300 mg/dL in improving response of depressive symptoms, defined as the proportion of subjects having a \geq 50% improvement in HDRS17 total score from baseline to the end of Week 12. (11) Assess the efficacy of sirukumab compared to placebo as adjunctive therapy to an antidepressant in subjects with MDD with screening hsCRP levels <0.300 mg/dL versus those with screening hsCRP levels $\geq 0.300 \text{ mg/dL}$ in achieving remission of depressive symptoms, defined as the proportion of subjects having a HDRS₁₇ total score ≤ 7 at the end of Week 12. (12) Evaluate whether hsCRP levels correlate with clinical efficacy as measured by the change from baseline to Week 12 in HDRS₁₇ total score.

Exploratory Objectives

(1) To explore the efficacy of adjunctive sirukumab compared to adjunctive placebo, based on the change from baseline to 12-week endpoint in the Inventory of Depressive Symptomatology – Clinician Rated 30 Item Scale (IDS-C30). (2) To explore immunesystem related biomarkers (hsCRP, cytokines, chemokines), as well as other mood disorder related biomarkers (growth factors, hypothalamic–pituitary–adrenal (HPA) axis markers, metabolic markers) and to explore the potential correlation between these biomarkers and the clinical response, non-response or safety parameters of sirukumab. (3) To explore genetic and epigenetic variation that may be related to clinical response, non-response, or safety parameters of sirukumab (4) To explore the effect of sirukumab on the pharmacokinetics of monoaminergic antidepressants. (5) To explore the relationship between the severity of childhood trauma as assessed through the Childhood Trauma Questionnaire and the change in HDRS₁₇ scores following adjunctive sirukumab or placebo.

1.2. Trial Design

This is a multicenter, double-blind, placebo-controlled study in male and female subjects, 21 to 64 years of age inclusive, with major depressive disorder (MDD) who have had a suboptimal response to standard oral antidepressant therapy; have failed no more than 3 antidepressant treatments in the current major depressive episode.

The study will consist of 3 phases: a screening phase of up to 4 weeks, a 12-week doubleblind treatment phase, and a 14-week posttreatment follow-up phase. The total duration of subject participation will be approximately 26 weeks.

1.3. Statistical Hypothesis for Trial Objective(s)

The primary hypothesis of this study is that sirukumab will determine significant improvement in depressive symptoms from baseline compared to placebo when administered as an adjunctive treatment to a monoaminergic antidepressant in the treatment of patients with MDD who have shown a suboptimal response to standard oral antidepressant therapy and have a screening hsCRP $\geq 0.300 \text{ mg/dL}$ (SI 3.00 mg/L), demonstrated by improvement in depressive symptoms from baseline to 12-week endpoint in the Hamilton Depression Rating Scale (HDRS17) total score.

1.4. Sample Size Justification

Approximately 192 subjects will be enrolled in this study, with approximately 96 subjects randomized per treatment group.

The target study population is male and female subjects with MDD who have had a suboptimal response to standard oral antidepressant therapy; have failed no more than 3 antidepressant treatments in the current major depressive episode; approximately 142 subjects with screening hsCRP $\geq 0.300 \text{ mg/dL}$ (SI 3.00 mg/L) and approximately 50 subjects with screening hsCRP<0.300 mg/dL (SI 3.00 mg/L) will be enrolled.

The expected final sample size of 142 for subjects with screening hsCRP ≥ 0.300 mg/dL (SI 3.00 mg/L) was determined based on the assumption of an effect size of at least 0.5 for the HDRS17 (mean change from baseline to week 12 endpoint between the sirukumab and placebo groups of 4 with SD=8). This is considered to be a clinically relevant difference in a population with suboptimal response to standard oral antidepressant therapy. Power is set at 90.0%, with a 1-sided alpha of 0.125 and a 12-week drop-out rate of 25%. It was also assumed that 10% of the randomized subjects would be excluded from the primary efficacy analysis due to having hsCRP ≥ 3.00 mg/L at screening but not at baseline.

1.5. Randomization and Blinding

Central randomization was implemented in this study. Subjects were randomly assigned to 1 of 2 treatment groups based on a computer-generated randomization schedule prepared before the study by or under the supervision of the sponsor. The randomization was balanced by using randomly permuted blocks and was stratified by country and 4 screening hsCRP levels: < 3.00 mg/L (0.300 mg/dL), $\geq 3.00 \text{ to } < 5.00 \text{ mg/L}$ ($\geq 0.300 \text{ to } < 0.500 \text{ mg/dL}$), $\geq 5.00 \text{ to } < 8.00 \text{ mg/L}$ ($\geq 0.500 \text{ to } < 0.800 \text{ mg/dL}$), and $\geq 8.00 \text{ mg/L}$ ($\geq 0.800 \text{ mg/dL}$). The interactive web response system (IWRS) assigns a unique treatment code, which dictates the treatment assignment and matching study drug kit for the subject. The requestor must use his or her own user identification and personal identification number when contacting the IWRS, and was then give the relevant subject details to uniquely identify the subject.

In general, randomization codes will be disclosed fully only if the study is completed and the clinical database is closed. At the interim analyses, the randomization codes and, if required, the translation of randomization codes into treatment and control groups will be disclosed to those authorized and only for those subjects included in the interim analysis.

2. GENERAL ANALYSIS DEFINITIONS

2.1. Treatment Groups

Unless specified, the treatment groups are labeled as 'Placebo' and 'Sirukumab'.

2.2. Pooling Algorithm

Five counties are planned to enroll subjects: US, Canada, United Kingdom, Poland and Russia. To account for country variability, country will be used as a factor in the statistical models to analyze efficacy.

2.3. Analysis Phases

There are 2 analysis phases defined in this study: Double-blind and Follow-up Phases. Each analysis phase has its own analysis reference start date and end dates.

2.3.1. Analysis Phase Start and End Dates

Double-Blind Phase

The analysis reference start date of the DB analysis phase is the date of the first dose of DB medication. The analysis reference end date of the DB analysis phase is the maximum of date of the last visit in the DB treatment phase or date of early termination from DB phase. For randomized subjects who did not receive any medication in the DB phase, the reference start date is missing.

Follow-Up Phase

The analysis reference start date of the Follow-up (Post-treatment) analysis phase is the day after the end of DB. The analysis reference end date is the maximum of the last follow-up visit date and end of trial date.

2.3.2. Study Reference Start and End Dates

The overall reference start date for the study is defined as the date of the first dose of DB medication (the date is missing for screened subjects who did not receive a dose of DB medication). The overall reference end date for the study is maximum of the last follow-up visit date and end of trial date.

2.3.3. Study Day and Relative Days

Study day is calculated relative to the overall reference start date for the study. Relative day is calculated relative to the analysis reference start date of the analysis phase in which the data are captured.

Study day for an event on or after the start of the study is calculated as:

Event date-study start date +1.

Study day for an event prior to the start of the study is calculated as:

Event date-study start date

Relative day for an event on or after a reference start date is calculated as:

Event date - reference start date + 1.

Relative day for an event prior to a reference start date is calculated as:

Event date – reference start date.

2.4. Visit Windows

As subjects do not always adhere to the protocol visit schedule, the following rules are applied to assign actual visits to protocol visits. Listed below are the visit windows and the target days for each visit. The reference day is Study Day 1 (which is the date of the first DB medication in the double-blind phase).

The baseline value is defined as the last observation before receiving the first dose of study drug on Day 1.

If a subject has 2 or more actual visits in one visit window, the visit closest to the target day will be used as the protocol visit for that visit window. If 2 actual visits are equidistant from the target day within a visit window, the later visit is used. If a visit window has no scheduled visits but does have unscheduled visits, then the unscheduled visit closest to the scheduled visit will be used. If a visit window has both a scheduled and an unscheduled visit, then a scheduled visit will have a priority even an unscheduled visit is closer to the target day.

All assignments will be made in chronological order. Once a visit is assigned to a visit window, it will no longer be used for a later time point except for the end point. Listed below are the visit windows and the target days (if applicable) for each visit defined in the protocol (Table 1).

Parameter	Scheduled Visit Time (label on output)	Time Interval (Day)	Target Time Point (Day)
HDRS ₁₇	Baseline	1/predose	1
	Week 1 (DB)	2 - 17	7
	Week 4 (DB)	18-42	28
	Week 8 (DB)	43 - 70	56
	Week 12 (DB)	71 - end of DB	84
CGI-S, IDS-C ₃₀ and	Baseline	1/predose	1
PHQ-9, SHAPS and	Week 1 (DB)	2 - 17	7
FACIT Fatigue	Week 4 (DB)	18-42	28
	Week 8 (DB)	43 - 70	56
	Week 12 (DB)	71 - end of DB	84
	Week16 (FU)	End of DB+1 - 133	112
	Week 22 (FU)	134 – end of FU	154
C-SSRS	Baseline	1/predose	1
	Week 1 (DB)	2 - 17	7
	Week 4 (DB)	18-42	28
	Week 8 (DB)	43 - 70	56
	Week 12 (DB)	71 - end of DB	84
	Week16 (FU)	End of DB+1 - 133	112
	Week 22 (FU)	134 – end of FU	154
Vital signs (BP, HR, RR,	Baseline	1/predose	1
temperature)	Week 4 (DB)	2 - 56	28
- ·	Week 12 (DB)	57 - end of DB	84
	Week16 (FU)	End of DB+1 - 133	112
	Week 22 (FU)	134 – end of FU	154
Body weight	Baseline	1/predose	1
	Week 12	2 - end of DB	84
	Week 22 (FU)	End of DB+1 – end of FU	154
Clinical laboratory	Baseline	1/predose	1
assessments: chemistry,	Week 4	2 - 42	28
hematology	Week 8	43 - 70	56
	Week 12	71 – end of DB	84
	Week 22	End of DB+1 – end of FU	154
Clinical laboratory assessments: urinalysis	Baseline	1/predose	1
~	Week 8	2 - 70	56
	Week 12	71 – end of DB	84
			1.5.4

2.5. Analysis Sets

Subjects will be classified mainly into the following analysis sets: all randomized analysis set, intent-to-treat analysis sets (with different variations) and safety analysis sets.

2.5.1. All Randomized Analysis Set

This analysis set will include all subjects who were randomized (i.e., subjects who reported a randomization date, or were assigned a randomization number) regardless of whether or not the treatment was received. This analysis set will be used for summarizing the overall study completion/withdrawal information using planned treatment group.

2.5.2. Efficacy Analysis Sets

Three analyses sets will be defined for efficacy analyses: the modified intent-to-treat 1 (mITT1), the modified intent-to-treat 2 (mITT2) and the modified intent-to-treat 3 (mITT3) analyses sets.

The mITT1 analysis set is defined as all randomized subjects with hsCRP \geq 3.00 mg/L at screening and baseline who receive at least 1 dose of study drug and have both the baseline and at least one postbaseline HDRS₁₇ total score measured within the double-blind treatment period.

The mITT2 analysis set is defined as all randomized subjects who receive at least 1 dose of study drug and have both the baseline and at least one postbaseline HDRS₁₇ total score measured within the double-blind treatment period.

The mITT3 analysis set is defined as all randomized subjects with hsCRP \geq 3.00 mg/L at screening who receive at least 1 dose of study drug and have both the baseline and at least one postbaseline HDRS₁₇ total score measured within the double-blind treatment period.

Subjects who receive an incorrect treatment will be analyzed under the planned treatment received.

2.5.3. Biomarker Analysis Set

Biomarker analyses will be performed on biomarker analysis set. It will include all randomized subjects who receive at least 1 dose of study drug in the double-blind phase and have at least 1 sample obtained.

2.5.4. Pharmacokinetic and Immunogenicity Analyses Sets

Pharmacokinetic analyses will be performed on pharmacokinetic analysis set. It will include all randomized subjects who receive at least 1 administration of sirukumab in the double-blind phase and have at least 1 sample obtained after sirukumab treatment.

Immunogenicity analyses will be performed on immunogenicity analysis set. It will include all randomized subjects who receive at least 1 administration of sirukumab and have appropriate samples for detection of antibodies to sirukumab (ie, subjects with at least 1 sample obtained after sirukumab treatment).

2.5.5. Safety Analysis Set

Safety analyses will be performed on the safety analysis set. It will include all randomized subjects who receive at least 1 dose of study drug in the double-blind phase. Analyses of change from baseline will include only subjects who have both baseline and at least 1 post-baseline observation during the double-blind phase.

Safety analyses for the follow up phase will be performed on the Safety (FU) analysis set. It will include all subjects who have at least 1 visit during the follow up phase.

Screen failures and randomized subjects who received no double-blind study medication will be excluded from the safety analysis set. Subjects who received an incorrect treatment will be analyzed under the planned treatment.

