7. SAFETY

7.1. Adverse Events

Adverse events (AEs) are coded using the MedDRA dictionary (version 17.0 or above). Treatment-emergent adverse events (TEAEs) that occurred in the double-blind phase will be summarized by system organ class, preferred term, and treatment group. Adverse events that occurred in the follow up phase will be summarized separately.

Adverse events in different phases of the study are defined as below:

- Treatment-emergent adverse events during the double-blind phase are defined as AEs with an onset during the double-blind phase. In other words, treatment-emergent AE during the double-blind phase should satisfy the condition: Double-blind start date/time ≤ AE onset date/time ≤ double-blind end date. If onset time is missing and AE onset date/time is the same as the double-blind start date/time, the AE is defined to be treatment emergent in the double-blind phase.
- Adverse events during the follow up phase are defined as AEs with an onset during the follow up phase. AEs during the follow up phase should satisfy the condition: (follow up phase start date \leq AE onset date/time and AE onset date \leq follow up phase end date).

A TEAE is an event that is new in onset or increased in severity following treatment initiation. An event that starts prior to, and ends after the initiation of study medication will be considered treatment-emergent only if the severity increases after the start of medication. Adverse events will not be considered treatment-emergent if they occur or increase in severity during the follow up phase. Adverse events occurring during the follow up phase will be summarized separately. In addition, AEs will be summarized by severity and relationship to study drug using the preferred term. For the summaries of AEs by severity/relationship to study drug, the observation with the most severe occurrence/closest relationship to study drug will be chosen if there is more than one incident of an adverse event reported during the analysis phase by the subject.

Serious AEs (SAEs) and AEs that lead to study discontinuation will be summarized separately by treatment group, system organ class, and preferred term. Data listings will also be generated for deaths, other SAEs, and discontinuations due to AEs.

Adverse Events of Special Interest

Clinically relevant TEAEs of special interest will be examined in malignancies, active TB, hepatobiliary abnormalities (as defined in the protocol), and gastrointestinal perforations.

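### A dosed subject who has an adverse event after the double-blind phase and attends no follow-up visit falls outside both the double-blind and the follow-up AE tables

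*SAP*

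**What the plan says.** Four rules in the SAP bear on this point.

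- **Phase dates (section 2.3.1).** The double-blind phase ends at the "maximum of date of the last visit in the DB treatment phase or date of early termination from DB phase". Follow-up begins the next day: "The analysis reference start date of the Follow-up (Post-treatment) analysis phase is the day after the end of DB". For its end, "The analysis reference end date is the maximum of the last follow-up visit date and end of trial date".
- **Treatment emergence (section 7.1).** "Adverse events will not be considered treatment-emergent if they occur or increase in severity during the follow up phase". These events go elsewhere: "Adverse events occurring during the follow up phase will be summarized separately". The same section identifies a follow-up AE by whether its onset lies between the start and end dates of the follow-up phase. It does not mention attendance.
- **Analysis sets (section 2.5.5).** The main safety set needs one dose of double-blind study drug. For the later phase, "Safety analyses for the follow up phase will be performed on the Safety (FU) analysis set", and of that set the SAP says: "It will include all subjects who have at least 1 visit during the follow up phase".
- **Serious events (section 7.1).** "Serious AEs (SAEs) and AEs that lead to study discontinuation will be summarized separately by treatment group, system organ class, and preferred term". This sentence names no phase and no analysis set. Listings of deaths, other SAEs and discontinuations due to AEs are also planned, with no stated restriction.

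**The concern.** The event definition and the population definition do not match. Whether an event belongs to follow-up depends on its date. Whether the subject is counted in follow-up depends on coming back. The two part company for a subject whose event is known, for example from a telephone report or a relative, but who is never seen again.

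Returning for a visit is a post-randomisation condition that can be related to the outcome being counted, since a subject who has died or is in hospital may be unable to attend. The main safety set has no such condition. An event during the double-blind phase counts for any dosed subject, while one shortly after it counts only if the subject later attends. Overall safety and tolerability is the first secondary objective in section 1.1, so the follow-up AE table should not depend on attendance.

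**Working it through.** The plan gives no figure for this point, so the check is a trace through the rules. Take a subject who received at least one dose, whose double-blind phase has ended, who attends no follow-up visit, and who has an AE with a known onset date after the double-blind phase.

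1. **Does the subject have a follow-up phase?** Yes. Under section 2.3.1 it starts the day after the double-blind phase ends, and the end-of-trial date alone can close it. No visit is needed.
2. **Is the event treatment-emergent?** No. Its onset is after the end of the double-blind phase (section 7.1; section 2.7 agrees). The double-blind end date is not extended by any lag after the last dose, so nothing draws the event back. It is not in the double-blind table.
3. **Is it a follow-up AE?** Yes by date, provided onset is on or before the end of the follow-up phase (section 7.1).
4. **Is it in the follow-up AE table?** No. Section 2.5.5 runs follow-up safety analyses on Safety (FU), and this subject is not a member.
5. **Is it in a by-arm SAE or discontinuation summary?** Undetermined. The section 7.1 sentence could be applied to all dosed subjects. It could equally be split by phase, in which case section 2.5.5 sends the follow-up part to Safety (FU).
6. **Is it in a listing?** Yes if it is a death, another SAE or an AE leading to discontinuation. For a non-serious AE that did not lead to discontinuation, section 7.1 names no listing.

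| Type of event after the double-blind phase, no follow-up visit | Double-blind AE table | Follow-up AE table | SAE/discontinuation summary | Named listing |
|---|---|---|---|---|
| Non-serious, no discontinuation | No | No | Not applicable | No |
| AE leading to discontinuation | No | No | Not secured | Yes |
| SAE | No | No | Not secured | Yes |
| Death | No | No | Not secured | Yes |

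There is one narrow exception. Under section 2.7, an AE whose onset day and month are both missing is counted as treatment-emergent in the double-blind phase. If only the day is missing, the imputed date (the first of the month, or the start of dosing) can also move an event back into that phase. Neither rule helps when the onset date is known.

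**The case against.** The strongest case on the other side is that the gap is narrow and easily overstated. Four points deserve an answer.

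*Serious events.* A reader might infer that a death or SAE in such a subject disappears from every safety summary. The SAP does not support that. The SAE sentence in section 7.1 names neither set nor phase, so a by-arm SAE table on all dosed subjects would be consistent with it, and the listings carry no restriction. What stands is that inclusion is not secured, and that a listing is not a by-arm count or rate.

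*Timing.* A reader might infer a blind window between Week 12 (target Day 84) and the first follow-up visit in Table 1 (Week 16, target Day 112), that is 112 − 84 = 28 days. There is none for anyone who attends. One visit, at Week 16 or Week 22, admits the subject to Safety (FU) with every follow-up AE from the first day of that phase. Table 1 also opens the Week 16 window on the day after the double-blind phase ends. Nor are early terminators lost as a group. An event with onset on or before termination is a double-blind event, and those who later attend are counted.

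*Size.* It is tempting to apply the 25% drop-out rate of section 1.4 to all 192 subjects, giving 0.25 × 192 = 48, and then to assume a share who never return. But the 25% is a planning assumption for the stratum with screening hsCRP of at least 3.00 mg/L, and the SAP gives no non-return rate. The product would also count subjects without a visit, not events lost. Because absent subjects leave both numerator and denominator, neither the direction of bias in the percentages nor a difference between arms is shown.

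*Meaning of visit.* The SAP does not define the word. If a telephone or end-of-trial contact counts, the gap shrinks. The protocol may settle this, but the SAP as written does not.

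After all four, the non-serious AE with a known date in a subject who never returns is still excluded. That follows from a stated rule, not from missing detail.

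**Conclusion.** The point holds in a limited form. Section 2.5.5 defines the follow-up safety population by attendance, while sections 2.3.1 and 7.1 define the phase and its events by date. For a dosed subject with no follow-up visit, a dated AE after the double-blind phase is in neither AE table. For deaths, SAEs and AEs leading to discontinuation, the defect is an unsecured place in the by-arm summaries; they would still be listed.

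The number affected cannot be derived from the SAP. It is confined to subjects who attend no follow-up visit and whose event is nevertheless reported with a usable date. The conclusion assumes that a visit means attendance and does not include every later contact. The change is worth making because it is cheap and the excluded events may be the ones that prevented attendance.

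**What to change.** In sections 2.5.5 and 7.1, state that AEs, SAEs and deaths with onset after the double-blind phase are summarised by onset date and treatment group on the full safety analysis set, meaning all dosed subjects except those known to have died during the double-blind phase. Apply this explicitly to the SAE and discontinuation summaries, so that their set and phase are no longer open. Report by arm how many of these subjects had no follow-up visit.

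The set should not be widened by admitting subjects because they have an AE record or have died. That would make the denominator depend on the outcome and inflate the rates. Measures that need a visit, such as laboratory tests and vital signs, can keep the attendance requirement.

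The cost is a short wording change and a revised dataset flag, with no new data. The downside is that follow-up percentages are slightly diluted by subjects with no follow-up information; the reported count of subjects without a visit lets the reader judge by how much.

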6.2. Immunogenicity Analyses

The incidence of antibodies to sirukumab will be summarized for all subjects who received at least 1 administration of sirukumab and have appropriate samples for detection of antibodies to sirukumab (ie, subjects with at least 1 sample obtained after sirukumab treatment).

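### Low priority: SAP 2.5.5 tabulates wrongly treated subjects under their planned arm for safety, a weak choice that matters only if dosing errors occur

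*SAP*

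**What the plan says.** Section 2.5.5 admits to the safety set every randomised subject with at least one dose of double-blind study drug. For dosing errors it adds: "Subjects who received an incorrect treatment will be analyzed under the planned treatment". The same section defines a separate Safety (FU) set for the follow-up phase.

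Section 7.1 builds the adverse event tables on treatment group, for example: "Serious AEs (SAEs) and AEs that lead to study discontinuation will be summarized separately by treatment group, system organ class, and preferred term". Section 2.1 labels the groups Placebo and Sirukumab without saying whether the label means planned or actual treatment, so section 2.5.5 decides the column. Section 3.5 summarises concomitant therapies in the safety set by planned group. No section provides a summary by treatment received.

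Two other sets are defined by what the subject actually received. For the pharmacokinetic set, section 2.5.4 says: "It will include all randomized subjects who receive at least 1 administration of sirukumab in the double-blind phase". For antibodies, section 6.2 says: "The incidence of antibodies to sirukumab will be summarized for all subjects who received at least 1 administration of sirukumab".

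**The concern.** Safety tables are read as a description of what happened to people exposed to the drug. Assigning the column by plan departs from that whenever the wrong kit is given:

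- **Placebo-assigned, given sirukumab.** Any later drug-related event is shown under placebo.
- **Sirukumab-assigned, given only placebo.** The subject stays in the sirukumab denominator although never exposed.

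If sirukumab raises the risk of an event, both errors reduce the displayed difference, which is the unfavourable direction for safety. The average effect on common events is slight. The case that matters is a single uncommon event in a misdosed subject. Section 7.1 names such events: "Clinically relevant TEAEs of special interest will be examined in malignancies, active TB, hepatobiliary abnormalities (as defined in the protocol), and gastrointestinal perforations".

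**Working it through.** No figure in the SAP is in dispute, so the check traces the rule and then sizes it.

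**Step 1: trace a subject through the sections.**

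| Subject | Safety tables (2.5.5, 7.1) | PK and antibody sets (2.5.4, 6.2) |
|---|---|---|
| Planned placebo, received sirukumab, later sample taken | Placebo column | Included |
| Planned sirukumab, received only placebo | Sirukumab column | Not included |

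Sections 2.5.4 and 6.2 settle who belongs to a set. The sentence in 2.5.5 settles which column a subject occupies. Both can be applied to the same subject without conflict.

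**Step 2: inputs for the size.** About 96 subjects per arm (section 1.4), all taken as dosed. The SAP gives neither event risks nor a number of dosing errors, so these are assumed: risks of 5% on placebo and 15% on sirukumab, with k = 1 or 5 placebo-assigned subjects on sirukumab throughout.

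**Step 3: expected difference under the planned-arm rule.**

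Placebo column = ((96 − k) × 5% + k × 15%) / 96

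- k = 1: (95 × 5% + 15%) / 96 = 5.10%; difference 15% − 5.10% = 9.90 points, against a true 10.0.
- k = 5: (91 × 5% + 5 × 15%) / 96 = 5.52%; difference 9.48 points.

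**Step 4: dependence on the assumed risks.** The formula reduces to true difference × (1 − k/96), so the relative shrinkage is k/96 whatever the risks: 1.0% for one subject and 5.2% for five.

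| Assumed risks (sirukumab, placebo) | True difference | k = 1 | k = 5 |
|---|---|---|---|
| 10%, 2% | 8.0 | 7.92 | 7.58 |
| 15%, 5% | 10.0 | 9.90 | 9.48 |
| 20%, 5% | 15.0 | 14.84 | 14.22 |

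The reverse error gives the same result. With one sirukumab-assigned subject on placebo only, the sirukumab column is (95 × 15% + 5%) / 96 = 14.90%, and the difference is again 9.90 points.

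**Step 5: one rare event.** A single event in a misdosed subject changes the column it is placed in by 1/96 = 1.04 points. For an event seen once or twice in the trial, that is a large part of what the table shows.

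**The case against.** The strongest reply is that the rule will seldom operate, is probably deliberate, and leaves other traces.

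- **Rarity.** Section 1.5 says: "The interactive web response system (IWRS) assigns a unique treatment code, which dictates the treatment assignment and matching study drug kit for the subject". Nothing in the SAP indicates that a dosing error occurred. This stands and is why the priority is low.
- **Deliberate use of the planned arm.** Section 2.5.1 uses it for disposition and section 3.5 for a safety-set summary. This shows consistency, but the rule still places exposed subjects in the unexposed column.
- **Visibility elsewhere.** Deviations (3.4), serum concentrations (6.1), deaths, serious events and discontinuations due to adverse events (7.1), and vital-sign abnormalities (7.3) are listed, so an affected subject may be noticed. This stands in part: the SAP does not say that any of these listings will set planned against actual treatment.
- **No test is affected.** Section 7 specifies summaries, not tests. This also stands.

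A reader might infer that 2.5.5 contradicts 2.5.4 and 6.2, because one subject can be placebo for adverse events and a sirukumab recipient for antibodies. The text does not support that. Only recipients can supply drug concentrations or antibodies to the drug, so membership by receipt is natural there and does not determine the safety column. A reader might also infer that a special-interest event would be visible only in a table. Section 7.1 does not say how those events will be examined, so that does not follow either.

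**Conclusion.** The point holds as criticism of an analysis choice, at low priority and only if dosing errors occur. When the rule in 2.5.5 operates, it puts events on sirukumab in the placebo column or unexposed subjects in the sirukumab denominator, and no section offers a view by treatment received. Under the assumed 5% and 15% risks, one fully misassigned subject costs about 0.1 of 10 points and five cost about 0.5. The practical risk is one rare or special-interest event in the wrong column, worth about 1 point. The error counts and risks are assumptions; the proportional shrinkage depends only on the number of misdosed subjects and the arm size.

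**What to change.** In section 2.5.5, replace the sentence on incorrect treatment with:

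> Safety analyses use the treatment actually received; a subject who received at least one sirukumab injection is analysed as sirukumab, and a subject who received only placebo as placebo. All subjects who received an incorrect treatment are listed with planned treatment, actual treatment by injection date, and all adverse events with onset dates.

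Apply the same treatment variable to the Safety (FU) set, which covers "a 14-week posttreatment follow-up phase". Change section 3.5 from planned group to treatment received. Otherwise one misdosed placebo subject would give denominators of 97 and 95 in the adverse event tables but 96 and 96 in the concomitant therapy table for the same set.

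Leave the treatment-emergent definition in section 7.1 unchanged, and do not remove events from both columns. Removing them would drop events that 7.1 says will be summarised while keeping the subject in the sirukumab denominator.

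The cost is one derived variable and one listing. If nobody was misdosed, no table changes. For a subject who received both treatments, events and values before the first sirukumab injection fall in the sirukumab column. With the dosing days in section 1.1, that is up to 28 − 1 = 27 or 56 − 1 = 55 days. The listing, with injection and onset dates, makes those events visible.
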